20.3. ECG EVALUATIONS

Results from the ECG will be based on the SAF analysis set, presented by DL (for **Part A only**)

The following ECG variables will be reported for this study:

Qualitative Evaluations:

- Overall assessment of ECG (Investigator's judgment Interpretation):
 - Normal
 - Abnormal - Not Clinically Significant;
 - Abnormal - Clinically Significant.

All the abnormalities – including the details of detected “Findings” as reported on electronic CRF - will be listed.

- RR Interval (msec);
- QT Interval (msec);
- QTc Interval (msec) – automatically calculated on electronic CRF using the Bazett's correction formula.

The following summaries will be provided for ECG data:

- The number (n) and percentage (%) from baseline by visit for qualitative interpretation;
- Actual and change from baseline by visit for quantitative measurements;

Document: PPD

Author: PPD

Version Number:

V2.2

Version Date:

21 March 2018

Template No: CS_TP_BS016 – Revision 3

Reference: CS_WI_BS005

Effective Date: 01May2012

Copyright © 2012 Quintiles Transnational Corp. All rights reserved.

The contents of this document are confidential and proprietary to Quintiles Transnational Corp. Unauthorized use, disclosure or reproduction is strictly prohibited.

- Shift from baseline according to markedly abnormal criteria for quantitative measurements;
- Listing of patients meeting markedly abnormal criteria for quantitative measurements;

ECG SPECIFIC DERIVATIONS

Bazett's Correction (msec) is derived directly from eCRF and it is calculated as follows:

$$o \quad QTc \text{ (msec)} = \frac{QT \text{ (msec)}}{\sqrt{RR \text{ (sec)}}}$$

Where, RR Interval, imputed directly on the eCRF by the investigator, is calculated as follows:

$$o \quad RR \text{ (sec)} = \frac{60}{HR \text{ (bpm)}}$$

ECG MARKEDLY ABNORMAL CRITERIA

Markedly abnormal quantitative ECG measurements will be identified in accordance with the following predefined markedly abnormal criteria:

- Absolute values for QTc interval > 450 msec
- Change from Baseline for QTc interval >30 msec increase from baseline

20.4. SPLEEN EVALUATIONS

Results from the Spleen evaluation will be based on the SAF analysis set and presented by Cohort (Part A only).

The following spleen variables will be reported for this study:

- Imaging Technique of Spleen:
 - MRI;
 - CT Scan.
- Qualitative Evaluation: Overall assessment of Spleen (Investigator's judgment Interpretation):
 - Normal;
 - Abnormal, Not Clinically Significant;

Document: PPD

Author: PPD

Version Number:

V2.2

Version Date:

21 March 2018

Template No: CS_TP_BS016 – Revision 3

Reference: CS_WI_BS005

Effective Date: 01May2012

Copyright © 2012 Quintiles Transnational Corp. All rights reserved.

The contents of this document are confidential and proprietary to Quintiles Transnational Corp. Unauthorized use, disclosure or reproduction is strictly prohibited.

- Abnormal, Clinically Significant.

The Abnormalities will be listed.

- Quantitative Evaluations:
 - Longitudinal Diameter (cm);
 - Antero/Posterior Diameter (cm);
 - Transversal Diameter (cm);
 - Splenic Volumetric Index (cm³) - automatically field on eCRF.

The following summaries will be provided for Spleen data:

- The number (n) and percentage (%) at baseline for Technique of Imaging;
- The number (n) and percentage (%) at baseline for qualitative interpretation;
 - The number (n) and percentage (%) at baseline, Cycle 3 Day 28 and Cycle 6 Day 28 showed a Spleen Volume reduction \geq 35%.

Spleen Specific Derivations: Splenic Volumetric Index (cm³) is automatically calculated by electronic CRF as following:

$$SVI (cm^3) = \frac{(Longitudinal * Antero/Posterior * Transversal) \text{ Diameters}}{27}$$

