2.3. EXPLORATORY OBJECTIVES

PART A AND B

- To evaluate the effect of Givinostat on single parameters of the clinical-haematological ELN response criteria [1].
- To evaluate the effects of Givinostat on PD markers.
- To evaluate the effects of Givinostat on spleen size (by MRI or CT scan) in patients with confirmed splenomegaly at baseline.
- To evaluate the effects of Givinostat on disease-related quality of life.
- To evaluate the effect of Givinostat on JAK2^{V617F} allele burden.
- To evaluate the reduction of the symptomatic treatment of pruritus.

PART B

- To evaluate the preliminary efficacy of Givinostat after 6 cycles of treatment according to the “new” ELN response criteria (i.e. the revised ELN response criteria).
- To evaluate the effect of Givinostat on single parameters of the “new” ELN response criteria (i.e. the *revised* ELN response criteria) [2].

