Document: PPD

Author: PPD

Version Number:

V2.2

Version Date:

21 March 2018

Template No: CS_TP_BS016 – Revision 3

Reference: CS_WI_BS005

Effective Date: 01May2012

Copyright © 2012 Quintiles Transnational Corp. All rights reserved.

The contents of this document are confidential and proprietary to Quintiles Transnational Corp. Unauthorized use, disclosure or reproduction is strictly prohibited.

In the patient listings all the additional ECG data have to be presented as soon as the first one.

- Spleen: Evaluation Date (to be reported only in the patient’s data listings), Imaging Technique (i.e. MRI, CT scan), Results Interpretation (Normal/Abnormal and Not clinically significant/Abnormal and Clinically Significant) and value of the following parameters:
 - o Longitudinal Diameter (cm);
 - o Antero-Posterior Diameter (cm);
 - o Transversal Diameter (cm);
 - o Splenic Volume Index (SVI, in cm³).

Notably, patients with splenomegaly performed the spleen evaluation as per site-specific clinical practice. Therefore, patients with splenomegaly before the treatment start are followed according to institutional guidelines (i.e. MRI, CT scan). The same imaging technique and the same instrument is used on a patient throughout the Study, *when possible*. No spleen evaluation is performed in splenectomised patients.

- Molecular Examination: Sample Collection Date (to be reported only in the patient’s data listings), Sample Accession Number (to be reported only in the patient’s data listings), Back-Up Sample Collection Date (to be reported only in the patient’s data listings), Back-Up Sample Accession Number (to be reported only in the patient’s data listings) and value of the following parameters:
 - o Positivity (Yes/No);
 - o Qualitative Evaluation (Homozygous/Heterozygous);
 - o Quantitative Evaluation (%).
- MPN-SAF Quality of Life Questionnaire: Completion Date (to be reported only in the patient’s data listings) and value (from a score 0 to a score 10) of the following parameters:
 - o Level of fatigue right NOW (i.e. at the completion of the MPN-SAF questionnaire);
 - o USUAL level of fatigue during past 24 hours (i.e. 24 hours before the completion of the MPN-SAF questionnaire);
 - o WORST level of fatigue during past 24 hours (i.e. 24 hours before the completion of the MPN-SAF questionnaire);
 - o Fatigue has interfered with General Activity during the past 24 hours (i.e. 24 hours before the completion of the MPN-SAF questionnaire);

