19. EXPLORATORY OUTCOMES

19.1. PARTS A AND B

The following exploratory parameters will be evaluated using ad-hoc descriptive analysis in **Parts A and B** based on ITT analysis set and PP analysis set:

- The effect of Givinostat on each single response parameter according to the clinico-haematological ELN (for PV and ET) [1] and EUMNET response criteria (for MF) [7]; note that only in case the enrolment in Part A is slow (i.e. < 5 patients enrolled in 3 months), the eligibility for this part of the study could be expanded to all patients with cMPN.
- Effects of Givinostat on PD markers.
- Effects of Givinostat on spleen size in patients with confirmed splenomegaly at baseline.
- Improvement of constitutional symptoms evaluated according to MPN-SAF QOL questionnaire [8, 9] including patients without the symptom of headache, pruritus and microvascular symptoms (i.e MPN SAF Score =0) and number and percentage of patient with symptom score from 0 to 3; from 4 to 6 and more than 7.

Document: PPD

Author: PPD

Version Number:

V2.2

Version Date:

21 March 2018

Template No: CS_TP_BS016 – Revision 3

Reference: CS_WI_BS005

Effective Date: 01May2012

Copyright © 2012 Quintiles Transnational Corp. All rights reserved.

The contents of this document are confidential and proprietary to Quintiles Transnational Corp. Unauthorized use, disclosure or reproduction is strictly prohibited.

- Reduction of the JAK2V617F allele burden, tested by quantitative RT-PCR.
- Reduction of the symptomatic treatment of pruritus in term of dosage and/or days of treatment.

The following exploratory parameters will be evaluated using ad-hoc descriptive analysis in Part B based on ITT analysis set and PP analysis set:

- The preliminary efficacy of Givinostat after 6 cycles of treatment according to the “new” ELN criteria (i.e. revised ELN response criteria) [2]. In all cases, the medical judgment of the Investigator’s is taken into account. In particular, if the Investigator’s clinical response assessment – that takes into account the overall medical judgment of the specific patient’s case - is not in agreement with the exact application of the revised clinico-haematological ELN response criteria , the Investigator’s assessment will supersede the “mathematical” application of these criteria and used for analysis into study report. Also mathematical application of ELN response criteria (not agreed by the medical site team) will be analyzed.

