- For titles and column labels, capitalize important words, i.e. nouns, pronouns, verbs, adverbs and adjectives but not articles, conjunctions or prepositions.
- All Footnotes will be in sentence case format.
- All symbols used in body of outputs will be footnoted.
- Continuous Variables:
 - Number (“n”),
 - Mean,
 - Standard Deviation (“SD”),
 - Median,
 - Minimum (“min”),
 - Maximum (“max”)

will be presented for all variables on the original scale.

- Categorical Variables:
 - Number (“n”),
 - Percentage (%)

in each category will be the default summary presentation.

- The percentage of patients in each category relative to the total number of patients in the relevant analysis population will be the default. Percentages relative to the total number of patients in the relevant analysis population with a non-missing assessment will be specified in a programming note on the shell if required.
- Where percentages are presented, a footnote will be added to explain what the denominator of the percentage is, in the form “Percentages are calculated relative to the total number of patients in the SAF” as the first footnote.
- All computed percentages will be presented using one decimal place except for where the percentage is 100 where no decimal places are presented.
- The percentage will be also presented if the count is zero.

Document: PPD

Author: PPD

Version Number:

V2.2

Version Date:

21 March 2018

Template No: CS_TP_BS016 – Revision 3

Reference: CS_WI_BS005

Effective Date: 01May2012

Copyright © 2012 Quintiles Transnational Corp. All rights reserved.

The contents of this document are confidential and proprietary to Quintiles Transnational Corp. Unauthorized use, disclosure or reproduction is strictly prohibited.

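### Section 20.4 puts the rate of spleen volume reduction of at least 35% on the Safety set, while the SAP defines the spleen effect in patients with splenomegaly at baseline

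*SAP*

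**What the plan says.** Three parts of the SAP bear on this percentage.

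- **Analysis set.** Section 20.4, under Other Safety Outcomes, reads: "Results from the Spleen evaluation will be based on the SAF analysis set". Section 5.1 defines SAF as all enrolled patients with at least one dose, whatever their spleen status.
- **The count.** The same section asks for "The number (n) and percentage (%) at baseline, Cycle 3 Day 28 and Cycle 6 Day 28 showed a Spleen Volume reduction" of at least 35%. The bullet names no denominator and no splenomegaly condition. Section 20.4 is the only section of the analysis text that specifies this count.
- **Default denominator.** Appendix 1 says: "The percentage of patients in each category relative to the total number of patients in the relevant analysis population will be the default". It also lets a programming note on the shell switch to patients with a non-missing assessment.

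Elsewhere the SAP restricts the spleen question. The exploratory objective in 2.3 concerns spleen size "in patients with confirmed splenomegaly at baseline". Section 7.5 uses the same restriction. Section 19.1 lists "Effects of Givinostat on spleen size in patients with confirmed splenomegaly at baseline", evaluated on ITT and PP.

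On who is scanned, section 10 states that "No spleen evaluation is performed in splenectomised patients". Section 3.7 (Amendment 2, item 8) says that in Part B all other patients are to have the evaluation.

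**The concern.** A volume-reduction responder rate measures treatment effect. The SAP says three times that the spleen effect is to be judged in patients who start with an enlarged spleen, yet the section that specifies the 35% count does not carry that restriction over. A programmer following 20.4 and Appendix 1 would divide by everyone dosed.

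Three kinds of patient would then sit in the denominator without belonging to the target population: those with a normal spleen at entry, those without a spleen, and any others in SAF without splenomegaly who were not rescanned. The first kind can also enter the numerator if a later scan reads smaller. The printed percentage would depend on the case mix at entry as well as on the drug, and it could not be compared with the splenomegaly-restricted results planned in 19.1.

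The same bullet lists baseline as a timepoint. Section 6.6 defines change as the visit value minus the baseline value, so a reduction at baseline is zero by construction.

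**Working it through.** The SAP gives no expected 35% rate, no share with splenomegaly and no sample size for this count, so there is no stated figure to reproduce. The check is how the percentage behaves under the two denominators.

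**Inputs.** N = 28 for Part B (sections 3.5 and 4). The share with splenomegaly is not given, so 25%, 50% and 75% are assumed. Responder numbers are also assumed and only illustrate.

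**Formula.** Let m be the number with baseline splenomegaly and x the responders among them. Let y be the responders among the other N − m patients.

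- Target rate = x/m
- SAF rate = (x + y)/N = (x/m)(m/N) + y/N

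If y = 0, the SAF rate is the target rate multiplied by m/N.

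**Results with y = 0** (exact 95% confidence intervals in brackets):

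| Assumed share | m | x | SAF rate x/28 | Target rate x/m |
|---|---|---|---|---|
| 25% | 7 | 2 | 7.1% (0.9–23.5) | 28.6% (3.7–71.0) |
| 50% | 14 | 5 | 17.9% (6.1–36.9) | 35.7% (12.8–64.9) |
| 75% | 21 | 7 | 25.0% (10.7–44.9) | 33.3% (14.6–57.0) |

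Under this condition the SAF rate cannot exceed 25%, 50% or 75% respectively, even if every patient with splenomegaly responds.

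**The opposite direction.** Sections 16.11 and 20.4 define the splenic volumetric index (SVI) as the product of three diameters divided by 27. A 35% fall leaves a ratio of 0.65, and 0.65^(1/3) = 0.866. A reading 13.4% smaller on each of the three axes is therefore enough for a normal spleen to count. In the middle row, y = 5 of the other 14 patients would bring the SAF rate back to 10/28 = 35.7%, equal to the target. The SAP has no figure for measurement variability, so y cannot be predicted.

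**The shell-note route.** With a non-missing denominator, splenectomised and unscanned patients drop out. Scanned patients with a normal spleen remain, because Part B scans them. The two rates still differ unless every scanned patient has splenomegaly or both groups respond at the same rate.

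**The case against.** The strongest reply is that the objective is already served. Section 19.1 plans spleen-size summaries and changes from baseline in the right patients on ITT and PP. No objective names a 35% responder rate. Section 20.4 is a safety section, where SAF is the rule, and its count is an added descriptive summary. The table gives n as well as the percentage, and listings include all scheduled data, so a reader could rebuild the restricted rate for at most 28 patients in Part B.

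Much of this stands. A reader might infer that the objective goes unanalysed, and 19.1 shows that it does not. What remains is that 19.1 does not carry the 35% count and 20.4 does not carry the restriction.

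Two other stronger readings are tempting.

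- **That the rate is certain to be divided by all of SAF.** The bullet names no denominator. Appendix 1 allows a shell note to change it and requires a footnote stating it, and the shells are not shown. The full-SAF denominator is only the default.
- **That the rate is necessarily diluted, by a known amount.** The share with splenomegaly and the response rates are not in the SAP, and shrinkage of normal spleens works against dilution. The size and net direction are open.

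The baseline timepoint is a small matter. A column of zeros misleads nobody, but it shows that the bullet needs rewording.

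**Conclusion.** The inconsistency is real. Section 20.4 puts the 35% volume-reduction count on SAF with no splenomegaly restriction, against the population set in 2.3, 7.5 and 19.1. Normal spleens are mixed in whichever denominator Appendix 1 yields. Splenectomised and unscanned patients are mixed in as well under the default.

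If only patients with splenomegaly respond, the printed rate is the target rate times the share with splenomegaly, which means half of it at an assumed 50% share (17.9% against 35.7% in the example). That size rests on assumed shares and responder counts. Any response among normal spleens reduces the gap, and the printed rate would exceed the target if the remaining patients responded at a higher rate than those with splenomegaly.

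The count is descriptive and exploratory, with no test or decision attached, and the Simon two-stage decision on the primary endpoint is untouched. The correction is still worth making, because it is cheap and the percentage as specified cannot be read as the effect that the SAP sets out to describe.

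**What to change.** In section 20.4:

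- Report the SVI reduction of at least 35% at C3D28 and C6D28 as n/m, with m the patients with confirmed splenomegaly at baseline, on ITT and PP as in 19.1. Cross-refer the two sections.
- State the criterion for confirmed splenomegaly. Use the local normal value where the site has supplied it; section 16.11 only recommends that sites do so. Otherwise use the investigator's baseline spleen interpretation, which the eCRF already collects.
- Print m and the number with a follow-up scan at each timepoint.
- Handle missing scans consistently with 7.3 and 17.2. Section 17.2 counts drop-outs due to drug-related TEAEs as non-response and does not replace other missing data. A blanket rule that every missing scan is a non-response would conflict with both sections.
- Drop the baseline timepoint for this count. Keep the SAF listing of all spleen data.

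The cost is SAP wording and one table shell, with no new data. The downside is a smaller denominator and a wider interval. In the 50% illustration, the exact 95% interval goes from 6.1–36.9% on 28 patients to 12.8–64.9% on 14.

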20.5. VITAL SIGNS

The following Vital Signs measurements will be reported for this study:

- Systolic Blood Pressure (mmHg);
- Diastolic Blood Pressure (mmHg);
- Heart Rate (bpm);
- Respiratory Rate (breaths/min);
- Body Temperature (°C);
- Height (cm), only for Baseline;
- Weight (kg);

Document: PPD

Author: PPD

Version Number:

V2.2

Version Date:

21 March 2018

Template No: CS_TP_BS016 – Revision 3

Reference: CS_WI_BS005

Effective Date: 01May2012

Copyright © 2012 Quintiles Transnational Corp. All rights reserved.

The contents of this document are confidential and proprietary to Quintiles Transnational Corp. Unauthorized use, disclosure or reproduction is strictly prohibited.

The following summaries will be provided for vital signs data:

- Actual and change from baseline by visit;
- Listings of all measurements by DL (for **Part A only**) and patient ID.

20.6. PHYSICAL EXAMINATION

The following summaries will be provided for physical examination data:

- Incidence of abnormalities at screening;
- Incidence of abnormalities post baseline.

20.7. OTHER SAFETY ASSESSMENTS

No other safety assessment will be collected for this study.

21. MOLECULAR ANALYSIS

Results from the molecular analysis performed during the Study will be listed, including results from pharmacodynamic (PD) markers.

The following information will be provided for JAK2^{V617F} allele burden evaluations:

- JAK2^{V617F} positivity (Yes/No);
 - Qualitative evaluation of JAK2V617F allele burden
 - Heterozygous
 - Homozygous
- Quantitative evaluation of JAK2V617F allele burden (%);
- Actual and change from baseline by visit;
- Number (n) and percentage (%) of patients with:
 - a reduction of any specific molecular abnormality to undetectable levels;

Document: PPD

Author: PPD

Version Number:

V2.2

Version Date:

21 March 2018

Template No: CS_TP_BS016 – Revision 3

Reference: CS_WI_BS005

Effective Date: 01May2012

Copyright © 2012 Quintiles Transnational Corp. All rights reserved.

The contents of this document are confidential and proprietary to Quintiles Transnational Corp. Unauthorized use, disclosure or reproduction is strictly prohibited.

- a reduction of $\geq 50\%$ from baseline value in patients with $< 50\%$ mutant allele burden at baseline;
 - a reduction of $\geq 25\%$ from baseline value in patients with $> 50\%$ mutant allele burden at baseline.
- Descriptive statistics of quantitative evaluation of JAK2^{V617F} allele burden.

Notably, approximately 4.0 mL of blood for PD markers is collected before the first Givinostat dose (pre-dose) and 12 hours after the first Givinostat dose (post-dose) at C1D1 both in **Part A** and in **Part B** for measurement of levels of molecular markers, to evaluate the PD effect of Givinostat and to identify markers predictive of clinical benefit of Givinostat (see [Appendix A](#) of the Study protocol). In addition, PD evaluations are performed also using an aliquot of the PK samples collected at time points described in the [paragraph 4.5.3.2](#) of the Study protocol. The molecular markers to be measured may include mRNA levels of JAK2, STAT5A, BclXL, PIM1, NFE2, LMO2, cMyc as well as HDAC3, STAT4, MYBL1, MEGF9, GLRX, FAM49A. The final list of PD markers to be measured will depend on ongoing scientific developments as well as availability of assays and other business considerations. For all time points an additional PD blood sample is collected as back-up sample.

This assessment is mandatory and is performed by a central laboratory. The exact date and time of the PD blood draws is recorded along with the date and time of the last dose of study drug preceding the blood draw.

All molecular examinations (e.g. JAK2^{V617F} allele burden evaluated by quantitative RT-PCR, mRNA isolation, gene expression) are performed in a central laboratory.

The results are transcribed into the electronic CRF by the central laboratory team or its designee and the original signed and dated laboratory print-out/tracings are monitored and stored at the central laboratory.

After evaluation of preliminary results and data exploration, some additional analyses may be performed to identify and quantify other molecular parameters of interest in term of improving of the knowledge of cMPN and the activity of the drug in these disorders.

JAK2^{V617F} allele burden (%) and changes (reductions) from baseline will be summarised using descriptive statistics (n, mean, SD, arithmetic CV (%), median, minimum and maximum) by dose level and time point.

A patient listing of all the relevant molecular examinations data (JAK2^{V617F} allele burden, mRNA isolation, gene expression) will be presented by DL (for **Part A only**) and time point.

Document: PPD

Author: PPD

Version Number:

V2.2

Version Date:

21 March 2018

Template No: CS_TP_BS016 – Revision 3

Reference: CS_WI_BS005

Effective Date: 01May2012

Copyright © 2012 Quintiles Transnational Corp. All rights reserved.

The contents of this document are confidential and proprietary to Quintiles Transnational Corp. Unauthorized use, disclosure or reproduction is strictly prohibited.

